10. HUMAN SUBJECTS

Subject Population

A total of 80 adults (40 patients with FM and 40 healthy volunteers), ages 18-65, will complete the behavioral portion of the study. We will match participants with FM and healthy control participants for age and sex at the group level. In addition, 20 adults (may be same or different individuals) will complete the pilot fMRI portion of the study. We will include all genders, races and ethnicities.

Inclusion Criteria:

All participants will be:

- 1) Between the ages of 18 and 65 years old
- 2) Fluent in English

Additional Inclusion Criteria for Chronic Pain Participants:

- 1) Reported diagnosis of Fibromyalgia (FM) by a physician, but no other chronic pain conditions of greater pain severity (diagnosis verified by medical records whenever possible)
- 2) Meets 2016 revised ACR diagnostic criteria (Wolfe, Clauw et al. 2016) for FM for more than 1 year (based on phone screen)

Additional Inclusion Criteria for Control Participants:

- 3) no indication of current pain or chronic pain (based on phone screen)

Exclusion Criteria:

- 1) Sensory, motor, or anatomic differences or injuries relevant to study procedures
- 2) Known anomalies of the central nervous system (including stroke, dementia, aneurysm, or personal history of psychosis)
- 3) Pregnancy
- 4) Inability to rate pain or sensations
- 5) Major medical conditions such as kidney, liver, cardiovascular (hypertension, preexisting cardiac arrhythmia), autonomic, pulmonary, or neurological problems (e.g., seizure disorder) or a chronic systemic disease (e.g., diabetes).
- 6) History of blood clots or clotting disorders
- 7) Current use of opiate medication(s)
- 8) Contraindications to MRI if participating in pilot MRI study
- 9) Unable to identify a heat stimulus 50C or lower that generates a rating of a 6 on our VAS scale
- 10) History of fainting or seizures
- 11) History of frostbite
- 12) Open cut or sore on hand to be immersed in cold water bath
- 13) Fracture of limb to be immersed
- 14) History of Reynaud's phenomenon (hands get white, then blue on exposure to cold, then red on warming)

We will recruit healthy controls (HC) that are group-matched to the chronic pain (FM) patients by age and sex.

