9. RESEARCH DESIGN AND METHODS

All procedures in this study are conducted solely for research purposes.

This proposed NIH-sponsored psychophysical and neuroimaging study includes two behavioral testing sessions, as well as one MRI session for a subset of participants. In this experiment we are studying sensory mechanisms supporting the modulation of pain by affective touch, and comparing them between individuals with and without the chronic pain condition Fibromyalgia (FM).

If the study will maintain a database for future uses (uses other than those specifically stated in this Research Plan), this must be clearly stated along with what information will be retained in the database and provide future examples of the potential future uses of the information.

Pre-Study Screening Procedures

Interested individuals will complete the phone screening. This includes demographic information as well as questions targeting inclusion and exclusion criteria (see Phone Screen Attachment).

Data Collection:

The following information will be collected from all participants: name, date of birth, age, gender, ethnicity, telephone number, email address, medical record number (will be deleted from study file once review of medical records is complete), diagnosis, condition, current/previous drug regimen, and handedness.

Consent & REDCap Intake

Prior to session 1, a member of the study team will email participants a REDCap link to digitally sign the consent form remotely. A member of the study team will schedule a phone or video call with participants to simultaneously discuss the consent form and answer any questions that may arise. After digitally signing the consent form and a HIPAA authorization form, history of their opiate use will be collected by asking participants to name every opiate medication they have taken previously and duration of use. Approximately one week prior to Session 1, participants will then be directed to REDCap to complete the following study questionnaires.

Study Assessments

Participants will complete the following questionnaires in REDCap:

- Chronic Pain Grade Questionnaire [16]
- Fibromyalgia Impact Questionnaire (Bennett, Friend et al. 2009)
- Childhood Trauma Questionnaire [17]
- Hospital Anxiety and Depression Scale (HADS) [18]
- Longing for Interpersonal Touch Picture Questionnaire [19]
- The Pittsburgh Sleep Quality Index (PSQI) [20]: This is a 10-item assessment designed to measure quality and patterns of sleep in adults.

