We expect that FM patients will show reduced pleasantness of C-LTMR-optimal touch compared to healthy individuals as found in FM patients in [3] and LBP patients in [8]. We hypothesize that current depression and trauma history will be significant predictors of blunted C-LTMR touch pleasantness. Based on an effect size F^2 of 0.15, three predictors, alpha of 0.05, and power 0.8, this study will require $N = 77$ participants. We will round up to $N = 80$ and include $N = 40$ FM patients and $N = 40$ healthy controls. Based on effect sizes observed in [3] and [8], this sample size will also be sufficient for the comparisons of pleasant touch.

Furthermore, we expect that FM patients will show reduced analgesic benefit of pleasant touch compared to healthy controls, due to reduced touch pleasantness ratings and our theorized relationship between touch pleasantness perception and analgesia, and due to reduced endogenous pain modulation evidenced in the CPM paradigm. We expect reduced analgesic effects of touch pleasantness in FM due to altered pleasant touch perception in FM (and LBP) [3, 8]. The studies showing analgesic effects of affective touch showed effect sizes of approximately $d = 0.6$ [6] and $d > 2$ (for the large compression area) [7], respectively. We would need 24 participants to demonstrate the smaller effect size in each group (alpha of 0.05, power of 0.8). No previous study has examined how pleasant touch modulates pain in chronic pain compared to healthy adults. To observe a difference in affective pain modulation between patients and healthy controls, based on the average large effect size of 0.78 seen across studies in [27] for CPM, this study would require 27 participants in each group, so the 40 participants calculated for each group will be sufficient. The MRI portion of the study will be a pilot study ($N = 20$), intended to provide preliminary data for future grant applications.

Data Analyses and Interpretation

Scores on the depression and trauma history questionnaires will be used as linear regressors to predict ratings of gentle brushing pleasantness.

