Cold- and Affective-CPM: We will average the pain ratings from each stimulus period and compare the percent change of baseline to post-test ratings as our primary outcome measure. We will use ANOVA to compare differences between baseline and post-test between touch types, within or between dermatomes/segments, and between patients and healthy volunteers. A linear regression will be used to determine whether baseline touch pleasantness ratings significantly predict the CPM effect for each type of touch.

ASL/fMRI: Periods of baseline pain will be contrasted with periods of touch concurrent to pain (test) and following pain (post-test) in brain areas involved in pain processing. Connectivity analyses will be performed to identify the source of significantly reduced pain response in any of these areas during affective touch.

Inclusion of Women and Minorities:

Participants will include all genders and races. Based on the latest San Diego-based demographic consensus, we plan to recruit 60% White, 16% Asian, 7% Black, .5% Native American, .5% Pacific Islander, 12% Other race, 5% two or more races. We expect that 29% of our participants will be Hispanic or Latino. If necessary to obtain minority representation, under-represented racial groups will be targeted specifically for recruitment.

Rates of FM are higher in females than in males (9:1 ratio) [28], so an approximately 9:1 ratio is expected in the current study. All races and ethnicities will be invited to enroll. Expected demographics are based on the latest San Diego-area demographic census. If needed, to increase minority representation, recruitment efforts will include targeted advertising (e.g., flyers, postings, community outreach presentations) in communities with high minority populations and through community-based talks given by the PI and staff.

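### Age and sex are matched only at group level and enter no named analysis; the between-person regressions get no protection from the matching, and adding both as covariates costs almost nothing

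*Combined protocol and SAP*

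**What the plan says.** Section 10 commits to the matching twice: "We will match participants with FM and healthy control participants for age and sex at the group level", and after the exclusion criteria, "We will recruit healthy controls (HC) that are group-matched to the chronic pain (FM) patients by age and sex". It gives no tolerance, strata or balance check. The eligible age range is wide ("Between the ages of 18 and 65 years old"). On sex, section 9 cites the higher rate of FM in women, "so an approximately 9:1 ratio is expected in the current study".

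Both variables will be on file, because the section 9 data-collection list for all participants includes "name, date of birth, age, gender, ethnicity, telephone number, email address". That list records gender, whereas the matching is on sex.

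The analyses are in section 9, Data Analyses and Interpretation:

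- Aim 1: "Scores on the depression and trauma history questionnaires will be used as linear regressors to predict ratings of gentle brushing pleasantness".
- Aim 2: the plan will "compare the percent change of baseline to post-test ratings as our primary outcome measure". For the comparisons themselves, one method is named: "We will use ANOVA to compare differences between baseline and post-test between touch types". That sentence goes on to add dermatome/segment and patient-versus-control comparisons.
- Pleasantness and analgesia: a linear regression of the CPM effect on baseline touch pleasantness, for each type of touch.

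None of these, nor the imaging analysis, names age or sex. The sample-size text in section 9 assumes three predictors, while the Aim 1 analysis names two. The third is not identified, so it cannot be credited as an adjustment for age or sex.

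**The concern.** Age and sex are thought important enough to recruit on and are then left out of every model. This has three consequences of unequal weight.

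1. **Regression slopes (the main concern).** Aim 1 asks whether depression and trauma predict blunted pleasantness. Aim 2 asks whether pleasantness predicts analgesia. Both rest on differences between individuals. Matching the FM group to the control group leaves age and sex free to vary with depression, trauma or pleasantness inside each group, so it removes none of that confounding.
2. **Patient-control contrast.** Group-level matching with no stated tolerance can leave some imbalance, which an unadjusted ANOVA carries into the group difference.
3. **Precision.** Variance that age and sex explain stays in the error term of the between-person comparisons.

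Prespecification is also at stake. If covariates are not fixed before the data are seen, the choice between adjusted and unadjusted results can be made afterwards.

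**Working it through.** **Inputs from the documents (sections 9 and 10).** 40 FM and 40 controls; ages 18-65; about 9:1 female to male; f² = 0.15 with three predictors, alpha 0.05, power 0.8, N = 77; d = 0.78 with 27 per group; d = 0.6 with 24 per group. Sidedness is not stated. Two-sided testing is used for the t tests because it reproduces 27 and 24.

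**Assumptions (not in the documents).** Share of outcome variance explained by age and sex, R² = 0.05-0.15 (0-0.20 in step 5); age-outcome correlation 0.2-0.4; ages spread evenly over 18-65.

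**1. The plan's own figures.** Overall F test, u = 3, v = N − 4, noncentrality 0.15 × N: N = 77, and power at N = 80 is 81.9%. Two-sample t, d = 0.78: 27 per group. Paired t, d = 0.6: 24. All three reproduce.

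**2. Regression slopes.** If a predictor has no true effect but age correlates with both predictor and outcome, the spurious correlation is the product of the two. Illustration with assumed correlations of 0.2-0.3 each: 0.2 × 0.2 = 0.04 to 0.3 × 0.3 = 0.09. At N = 80 a nominal 5% test then rejects about 6.4% to 12.6% of the time.

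**3. Patient-control contrast.** Age SD for a flat range = (65 − 18)/√12 = 13.6 years. Bias in SD units = (age gap/13.6) × r.

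- Gap of 3 years, r = 0.2: 0.22 × 0.2 = 0.04 SD; type I error about 5.4%.
- Gap of 5 years, r = 0.4: 0.37 × 0.4 = 0.15 SD; type I error about 10.0%.

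With no matching at all, the standard error of the difference in mean age is 13.6 × √(2/40) = 3.0 years. Gaps of 3 and 5 years are therefore 1.0 and 1.6 such standard errors, so these cases describe matching that has largely failed.

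If the matching is exact, an unadjusted test is slightly conservative: true type I error is about 4.4%, 3.9% and 2.9% at R² = 0.05, 0.10 and 0.20.

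**4. Precision.** Standard-error ratio = √[(1 − R²) × 78/76], which charges the 2 degrees of freedom.

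| R² | SE ratio | Fall in SE | Equivalent N = 80/ratio² |
|---|---|---|---|
| 0.05 | 0.987 | 1.3% | 82 |
| 0.15 | 0.934 | 6.6% | 92 |

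**5. Power of the group comparison, 40 per group.**

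| | Unadjusted | Adjusted, R² = 0 | 0.05 | 0.10 | 0.20 |
|---|---|---|---|---|---|
| Power, d = 0.78 | 93.1% | 93.1% | 94.2% | 95.3% | 97.1% |
| Power, d = 0.6 | 75.5% | 75.5% | 77.6% | 79.8% | 84.2% |
| Detectable d, 80% power | 0.634 | 0.635 | 0.618 | 0.602 | 0.568 |

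**6. Effect of the change on the regression sample size.** Testing three predictors given age and sex (u = 3, v = N − 6, f² = 0.15 read as the effect given those covariates): N = 77, power 81.8% at N = 80. Testing all five predictors jointly at f² = 0.15: N = 92, power 73.2% at N = 80.

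**The case against.** The best case for leaving the plan alone has four parts.

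- **The matching is a real commitment.** It is stated twice, and if carried out it leaves little age bias in the group contrast. With about four men per group expected, there is also little room for sex imbalance. This stands. A reader might infer that the patient-control comparison is seriously confounded. The documents do not support that: the larger bias figures need matching that barely works, and even 0.15 SD is well below the planned d of 0.78.
- **The design already removes some of the variation.** Heat is calibrated to each person's rating of 6 out of 10, and the primary outcome is change from that person's own baseline. This may well put R² for the CPM outcomes at or below the low end of the assumed range. It does not apply to Aim 1, where the outcome is a pleasantness rating.
- **Precision is not lost everywhere.** A reader might infer that every error bar in the study is too wide. It is not so. Touch type and segment are compared within person, and between-subject covariates do not reduce that error. The hypothesis that touch lowers pain is likewise a within-person comparison, not confounded by age or sex.
- **The third predictor could be an adjustment.** The text does not say what it is. It cannot be counted as age or sex, and one predictor could not be both.

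None of this answers the point about the regressions, which group matching does not protect whatever its quality.

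**Conclusion.** The point holds in this limited form. The omission is certain from the text. Its size is not, because the documents give neither the variance explained by age and sex nor the imbalance that matching will leave.

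The case is strongest for the Aim 1 and pleasantness-CPM regressions, where matching gives no protection. How much confounding is present there is unknown, and the 6.4-12.6% error rates are an illustration only. For the patient-control contrast, bias should be small if matching works. The precision gain is modest (standard errors down about 1-7%, about 82-92 equivalent participants) and confined to between-person comparisons.

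A reader might also infer that the sample size is wrong. It is not: 77, 27 and 24 all reproduce, and none needs to change if the covariates are handled as described under the fix. The change is worth making because it is nearly free, not because the results would otherwise be unusable.

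**What to change.** In section 9, Data Analyses and Interpretation:

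1. Prespecify age (continuous) and sex as covariates in the Aim 1 regression, in the between-group part of the Aim 2 analysis, and in each pleasantness-CPM regression. Report unadjusted results as a sensitivity analysis.
2. State that the hypothesised predictors are tested by partial tests given age and sex, not by a joint test of all five terms. The first keeps N = 77; the second would need N = 92.
3. Name the third predictor assumed in the sample-size text.
4. Say which variable is used for both matching and adjustment, since section 10 refers to sex and the data-collection list to gender.

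Cost: a few sentences of analysis-plan wording and 2 degrees of freedom. No change to recruitment, procedures or sample size is needed. At about 9:1 the sex coefficient will be estimated imprecisely (about four men per group of 40), so it should serve as an adjustment term and not be interpreted. If age and sex explain nothing, group-comparison power at d = 0.78 stays at 93.1%.

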11. RECRUITMENT AND PROCEDURES PREPARATORY TO RESEARCH

Subjects will be recruited through four primary methods: (1) from IRB approved flyers and recommendations by UCSD study physicians, (2) the ResearchMatch website, (3) via patient information extracted from EPIC, and (4) through web advertisements on social media and websites. We will begin study recruitment after we have completed all NIH oversight requirements.

- 1) We may post IRB approved flyers throughout the community and UCSD Pain Medicine physician offices. If a physician believes a patient is qualified for this study, they will refer the potential participant

to the flyer at which point they can voluntarily contact the research team to assess eligibility. In addition, the treatment physician may approach the participant and introduce the study. The treating physician will further discuss the research study with the potential participant and refer them to the research team's contact information, at which point the patient has the discretion to contact the study staff. There will be no direct contact of the potential research subject by the study staff unless prompted by the potential subject. Their treating physicians can refer them to our study and they will call us, if they choose, on their volition. We will not access medical records until after we have permission.

- 2) The study may be advertised on ResearchMatch to gain interest for participation. This site will allow for members of the community to inquire as to their potential interests in the study's goals and requirements.
- 3) We may request a Data Extraction Concierge Service (DECS) through the ACTRI. The service will allow ACTRI staff to extract patient information from Epic and find participants that may be eligible to participate in the study. The exported data will include: patients' MRN, name, phone number, mailing address, and email address. These patients may be contacted by phone, a mailed hard copy letter, and/or by email (containing no PHI). No more than two methods will be used per patient (methods will depend on response rate we identify in practice).
- 4) We may post study advertisements on social media and websites either ourselves, or through BuildClinical. BuildClinical is a data-driven platform that helps academic researchers recruit participants for research studies more efficiently using social media, software, and machine learning. They have worked with IRBs in the U.S. to ensure they adhere to all the appropriate guidelines and procedures and are approved and currently in use by multiple colleagues in the UC San Diego School of Medicine. They utilize study-specific advertisements to engage participants on digital platforms such as Facebook, Google, WebMD, etc. and redirect them to a study-specific landing page should they click it. On the landing page, the person can complete an online pre-screen questionnaire that gets routed into BuildClinical's platform. BuildClinical's Secure Socket Layer (SSL) software, which encrypts all inputted information, keeps participant information private, and is HIPAA compliant. Their backend servers are stored in the USA at some of the most secure data centers in the world. This strategy will allow us to target potential chronic pain participants and provide preliminary screening procedures for individuals who may be eligible to participate in the study. Contact information will include name, phone number, and email. BuildClinical retains the information in their portal throughout the duration of the contract. Upon termination of service, the information is deleted from the portal and it may be downloaded as an excel file to keep for our records. The information is transferred through their HIPAA Compliant platform that encrypts all data in transit and at rest. There is 2 factor authentication available for use and every researcher will have their own unique login credentials. Ad targeting will be for ages within our 18-65 range and for the San Diego geographic region. BuildClinical will refine ad targeting based on the profiles of persons who click on initial ads. We have uploaded as supplementary materials our lab's social media ad as well as all materials from BuildClinical (screening form, ad copy, ad creatives, and landing page).

When a potential subject contacts our lab, a brief subset of preliminary eligibility criteria (such as age, gender, etc.), will be reviewed by study personnel to determine subjects' preliminary eligibility for the research study during the phone screening and Visit 1. The attached phone script will be employed to identify preliminary study eligibility. The study team member screening potential subjects will obtain verbal consent before any subject information is collected. See item 12 below for request for waiver of documented consent for this screening. Subjects who fulfill the preliminary eligibility criteria will be offered further participation in this study.

Preliminary eligibility may be determined at the time of phone screening, but formal eligibility will only be determined after informed consent is obtained and a standard, stand-alone HIPAA authorization form is

signed. Standard HIPAA authorization to collect research data from the subject's medical record will be obtained at the time of informed consent during Session 1. Only subjects who have consented and provided HIPAA authorization will have identifiers or linked information (e.g., subjects initials, study numbers, etc.) recorded on the Screening/Enrollment Log. The Screening/Enrollment Log is necessary to keep track of who the subjects enrolled in the study are, and record their responses to the screening questions for use in describing the study sample in any resulting publications. No entries will be made in the Screening/Enrollment Log for individuals who do not pass screening or do not consent and provide HIPAA authorization. The study funder (NIH) will not have access to the subject's PHI. Only team members, as described in item 21, will have access to this information.

Strategies: Diversity and reflection of regional population. Geographically, the clinics at the Altman Clinical and Translational Research Institute service a broad portion of the greater San Diego region. As a result, our study coordinators will recruit patients from a highly diverse patient population in terms of race, gender, and socioeconomic status. Subject populations in previous and ongoing studies have reflected the diversity of the region and disease-specific demographics. If we are unable to obtain sufficient minority representation in our sample, under-represented racial groups will be specifically targeted for recruitment.

Contingency plans: Should the above streams of recruitment prove inadequate for us to meet our accrual timetable and keep our cohort schedule on track, we will reach out to social media and other local print and multi-media-based advertisement strategies prominent within the San Diego area. This approach has proved useful in past studies and should do so again. Participants will also be reimbursed for successful study completion. This approach has been useful in motivating participants to complete their study responsibilities in the past. If we find that the amount offered is inadequate for maintaining active subject engagement, we will consider increasing it.

These recruitment plans have been very successful at attaining targeted sample sizes in previous studies and have been recognized by UCSD and the NIH as appropriate models for recruitment success. The Research Plan will be amended to include these recruitment strategies or materials as they are added but prior to their use.

ResearchMatch message text is submitted separately. Other recruitment materials that are not included in this submission will be submitted to and approved by the IRB prior to use.

